
**The following documents are currently attached to this item:**

*There are no documents attached for this item.*

**Deception**

Does your project use deception?

No

**International Research**

Are you conducting research outside of the United States?

No

**Analysis Plan**

Categorical variables will be analyzed using chi-squared or Fishers exact test and parametric or non-parametric t-tests for continuous variables. Bivariable analysis will be used to determine variables (risk factors) that are independently associated with post-operative UTI. Duration of catheterization between groups will be compared using the Mann-Whitney test to compare difference in medians. The primary outcome will be the rate of clinically suspected UTI requiring treatment within the first three weeks following surgery. Comparison with fluoroquinolones will be performed using relative risk ratio. Analysis will be performed by intention to treat. If imbalances in baseline demographics are identified, multivariate analyses for post-operative UTI will be performed to control the inequality. Cost-effectiveness analysis will be performed by monetizing the collected resource utilization data in each treatment arm, including use of intervention resources, UTI treatment resources, as well as primary and secondary care resources. Incremental cost-effectiveness ratios will be calculated to compare difference in costs between prophylaxis with methenamine and prophylaxis with fluoroquinolones to the difference in effect on the incidence of post-operative UTI. Prevalence of adverse effects will be measured as

percentages. Rate of urine cultures performed by patients treated for symptomatic UTI, as well as the rate of culture-positive UTI will be noted; comparison with fluoroquinolones will be performed using relative risk ratio, with analysis by intention to treat. Positive cultures will be analyzed for percentage of uropathogen type, type of uropathogen showing resistance, and overall percentage of cultures showing resistance.

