### **Accrual**

This trial will be an non-inferiority trial, intended to determine if a short course of methenamine hippurate is no worse than a short course of fluoroquinolones (ciprofloxacin at Pennsylvania Hospital, levofloxacin at HUP, based on current practice and fluoroquinolone availability at each site) in prevention of post-operative UTI in short-term indwelling catheterization. Our primary outcome is the treatment of UTI by symptoms, a clinically relevant outcome. In the only study to look at this primary outcome after treatment with prophylactic antibiotics during short-term catheterization in urogynecologic surgery, the percentage of patients requiring treatment for UTIs after prophylactic antibiotics was 22%. If we assume a non-inferiority margin of 15%, a clinically relevant margin and commonly used in non-inferiority/equivalence trials for studies examining antibiotic use for urinary tract infections, as well as 80% power and a one-sided alpha of 0.025, 120 participants in each arm (total of 240 patients) will be required. Of all patients that undergo pelvic reconstructive surgery at our institution, approximately 75% are discharged home with an indwelling catheter. With a potential 15% drop-out rate, we therefore anticipate that we will need to recruit about 370 eligible patients in our clinics. As listed before, review of the surgeons logs over the last 12 months shows that this study is feasible due to the large volume of pelvic reconstructive surgery procedures in Urogynecology and Urology. Last year, the combined surgical volume of these cases at our three clinics was 532 subjects; thus, we anticipate we will be able to easily recruit the proposed sample size in one year. We plan to

recruit women from 4 sites in 3 departments in the University of Pennsylvania Health System: 1) Urogynecology at Hospital of University of Pennsylvania (HUP), 2) Urogynecology at Pennsylvania Hospital (PAH) and 3) Urology at Pennsylvania Hospital (PAH). Physician investigators are present at all three sites, and will have opportunity to screen patients planning for surgery for pelvic organ prolapse, urinary incontinence, or both, for participation.

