**Procedures**

**RECRUITMENT** We plan to recruit women from 3 clinical sites associated with 3 departments in the University of Pennsylvania Health System: 1) Urogynecology at Hospital of University of Pennsylvania (HUP), 2) Urogynecology at Pennsylvania Hospital (PAH) and 3) Urology at Pennsylvania Hospital (PAH). Physician investigators, who are present at all sites, will screen patients planning for surgery for pelvic organ prolapse, urinary incontinence, or both, for participation. Following confirmation of eligibility, the physicians will obtain informed consent prior to surgery at the planned preoperative visit. Last year, the combined surgical volume of these cases at our three clinics was 532 subjects; thus, we anticipate we will be able to easily recruit the proposed sample size in twelve months. **ENROLLMENT AND BASELINE VISIT:** Patients who are being discharged home with an indwelling catheter following pelvic reconstructive surgery will be enrolled into the study. With regards to outpatient surgery (such as a suburethral sling), this will occur within a few hours after surgery for patients who fail their trial of void. Following inpatient surgery (such as sacrocolpopexy, uterosacral or sacrospinous ligament fixation, or colpocleisis), patients who are being discharged from the hospital with an indwelling catheter will be enrolled into the study. As per standard of care, all subjects will be scheduled for an office visit for catheter removal 24 to 72 hours after placement of the indwelling catheter per surgeon preference. Demographic information will be collected from the patients medical record (age, menopausal status, concurrent estrogen use, ethnicity, level of education, medical comorbidities, history of recurrent UTIs, and duration of hospitalization). Data regarding the patients surgical intervention (procedure type, surgical complications, operative time) will be collected from the operative record. At the time of catheter removal, subjects will be randomized to either methenamine hippurate or fluoroquinolones, using sealed, opaque, sequentially numbered envelopes. All patients, and all physicians and nurses directly involved in patient calls and clinical interaction, will be masked to treatment allocation. Only the nurses involved in catheter removal, but not decisions on the primary outcome, will open the envelope, and distribute the allocated medication to the patient, who will take one dose at the office. A 24-hour course of fluoroquinolones, as per AUA guidelines, are the first-line antibiotics for catheter removal, and will be one of the active arms of the study. Due to differences of office practice and formulary availability, the fluoroquinolone of choice at each site will be different; this is clinically relevant as different urology practices across the country use different fluoroquinolones for prophylaxis. At HUP and Radnor, the 24 hour course of fluoroquinolone used will be one dose of 500 mg of levofloxacin, as per office practice and formulary availability. At the other sites (Pennsylvania Hospital, Chestnut Hill Hospital), the 24 hour course of fluoroquinolone as per office practice will be two doses of 500 mg of ciprofloxacin, 12 hours apart. Methenamine hippurate will be given as two doses of 1g of methenamine hippurate, taken 12 hours apart. The patient will not be told which

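### Bivariable tests cannot show that a risk factor is independently associated with post-operative UTI, so this ancillary analysis can mislabel correlated factors

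*Combined protocol and SAP*

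**What the plan says.** The Analysis Plan gives the risk-factor analysis one sentence: "Bivariable analysis will be used to determine variables (risk factors) that are independently associated with post-operative UTI". The general tests are set out just before it: "Categorical variables will be analyzed using chi-squared or Fishers exact test and parametric or non-parametric t-tests for continuous variables". Each of these relates two variables only, as does the Mann-Whitney comparison of catheter duration between groups.

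The one multivariable step follows later in the same section: "If imbalances in baseline demographics are identified, multivariate analyses for post-operative UTI will be performed to control the inequality". No covariate list, selection rule or second modelling stage is given for risk factors.

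The likely candidates are in the Procedures section. From the medical record: "age, menopausal status, concurrent estrogen use, ethnicity, level of education, medical comorbidities, history of recurrent UTIs, and duration of hospitalization". From the operative record: "procedure type, surgical complications, operative time". The Objectives and the Secondary outcome section mention factors only in connection with medication compliance. UTI risk factors are listed in neither.

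**The concern.** An independent association is one that remains once the other relevant factors are held fixed. A one-factor test does not hold anything fixed. If a factor with no effect of its own travels with one that does affect UTI, the crude test picks up the shared part.

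The candidate list makes such overlap plausible. Age and menopausal status are related. The Procedures section separates outpatient surgery, such as a sling, from inpatient surgery, such as sacrocolpopexy, so procedure type and hospital stay are linked by design, and operative time probably follows procedure. Catheter removal is scheduled 24 to 72 hours after placement by surgeon preference, so catheter duration may follow surgeon and procedure. The Background puts bacteriuria risk at 5-10% per catheter day, which makes duration a plausible true driver.

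At stake is the wording of a secondary report. Readers who see *independent* will take it that adjustment was done.

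**Working it through.** **1. The plan's own figure.** The Accrual section assumes a 22% event rate, a 15-point margin and "80% power and a one-sided alpha of 0.025". With equal true rates and unpooled variance, n per arm = (1.96 + 0.8416)² × 2 × 0.22 × 0.78 / 0.15² = 7.849 × 0.3432 / 0.0225 = 119.7, so 120 per arm and 240 in total. This matches the plan. The plan states no figure for the risk-factor analysis.

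**2. Does another sentence supply the adjustment?** The multivariable step is triggered by imbalance in baseline demographics, and its purpose is to control that imbalance. Two risk factors can be strongly correlated with each other while both are evenly spread across the arms. The model may therefore never be fitted, and if it is, it addresses a different question.

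**3. How often can a null factor be flagged?** The effect sizes and correlations here are assumptions, since the documents give none. Take n = 240 and logit P(UTI) = −1.40 + ln(OR) × C, with C standardised, giving an event rate of about 20% to 21%. Factor A has correlation ρ with C and no effect of its own. Tests are two-sided at 0.05, with 3,000 simulated datasets per setting. Share of bivariable tests that flag A:

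| OR per SD of C | ρ = 0.2 | ρ = 0.4 | ρ = 0.6 |
|---|---|---|---|
| 1.2 | 5.6% | 6.7% | not run |
| 1.3 | 6.1% | 9.4% | 15.1% |
| 1.5 | 7.9% | 17.7% | 31.5% |
| 1.8 | 12.2% | 29.7% | 58% |

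With A and C in one model, A was flagged in 4.4% to 5.9% throughout. With ρ = 0 both methods stay near 5%. Repeat runs of the strongest setting fell between about 55% and 58%.

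A hand check agrees. The crude log odds ratio for A is roughly ρ × ln(OR), with standard error about 1/√(n·p·(1 − p)).
- OR 1.8, ρ = 0.6: 0.6 × 0.588 = 0.353; SE = 1/√(240 × 0.21 × 0.79) = 0.158; z = 2.23; chance of flagging about Φ(2.23 − 1.96) = 60%.
- OR 1.3, ρ = 0.2: 0.2 × 0.262 = 0.052; SE = 1/√(240 × 0.20 × 0.80) = 0.161; z = 0.33; chance of flagging about 6%, counting both tails.

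**4. The same with binary factors.** Assumed prevalences are 30% for C and 40% for A, overall risk 22%, C–UTI odds ratio 1.5 to 4, A–C odds ratio 1 to 8, with 2,000 trials per setting. Bivariable flagging ran from 4.3% to 49.7%, and adjusted flagging from 4.3% to 5.9%.

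**5. How large a model can the trial carry?** Applying 22% to both arms, expected events are 0.22 × 240 = 52.8, about 53. At an assumed ten events per parameter that is 52.8 / 10 = 5.3, so about five parameters. Multi-category factors use these up quickly. Arm, recurrent-UTI history, age and catheter duration take 4. Procedure type coded in full (sling, sacrocolpopexy, uterosacral, sacrospinous, colpocleisis) adds 4. The four sites named in the Procedures section (HUP, Radnor, Pennsylvania Hospital, Chestnut Hill) add 3. The total is 11, or 52.8 / 11 = 4.8 events per parameter.

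**The case against.** The strongest reply is that little depends on this. UTI risk factors are in neither the aims nor the secondary outcomes. The non-inferiority comparison, the sample size and the cost, resistance and adverse-effect analyses do not use the result. That stands, and it keeps the point minor. A reader might infer that the trial's main conclusion is at risk; the documents do not support that.

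A reader might also infer that the plan *will* report confounded factors as independent. That is too strong. Mislabelling requires a null factor that is correlated with a true risk factor of sufficient strength, and the documents give neither the correlations nor the odds ratios. In the weak settings above, the bivariable test flags barely more than 5%.

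A charitable reader could take the bivariable tests as a screen before a model. The text does not bear this out, because no second stage is described.

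Finally, a new model can be called a reviewer's preference. That is fair: for an analysis outside the stated aims, correcting the wording is enough.

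**Conclusion.** The sentence is wrong as written: the method named cannot establish the property claimed, and nothing else in the plan supplies it. The consequence is possible mislabelling, not certain mislabelling. Under the assumed range (odds ratio 1.2 to 1.8 per SD, correlation 0 to 0.6, 240 women), a null factor is flagged in about 5% to 55-58% of bivariable tests, against about 5% to 6% with joint modelling. The upper end belongs to the strongest assumed setting and is not a forecast for this trial. The logical point does not depend on any of these inputs. The fault is confined to an ancillary analysis and is of low severity.

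**What to change.** Delete *independently* from the sentence, and state that bivariable results will be reported as unadjusted and exploratory. This is one sentence, needs no new data, and resolves the contradiction in full.

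If independent associations are wanted, pre-specify one multivariable model for post-operative UTI. Limit it to about five parameters in total, counting treatment arm and each non-reference level of any multi-category factor. Use factors known before randomization, such as history of recurrent UTI, age, and catheter duration up to the first removal. Total catheter duration is unsuitable without qualification: randomization takes place at catheter removal, and the Procedures section allows a catheter to be replaced after a failed voiding trial, so part of the total can fall after randomization. Report adjusted estimates with 95% confidence intervals as exploratory.

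The cost of this option is one model on data already collected, and fewer factors can be assessed.

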**Objectives**

**Overall objectives**

SPECIFIC AIMS Primary Aim: To determine if the efficacy of prophylaxis with a 24 hour course of methenamine hippurate (two doses) is non-inferior to the efficacy of a 24-hour course of fluoroquinolones in prevention of post-operative urinary tract infections after short-term indwelling catheterization following surgery for pelvic floor disorders. Secondary aim: - To determine if prophylaxis with methenamine hippurate is more cost-effective than prophylaxis with fluoroquinolones

in patients undergoing short-term indwelling catheterization. - To determine the antibiotic resistance profile of post-operative urinary tract infections that develop after short-term indwelling catheterization after surgery for pelvic floor disorders, with methenamine as compared to fluoroquinolones. - To determine the prevalence of side effects that may accompany use of methenamine hippurate prophylaxis. - To describe factors that influence patient medication compliance with short-term methenamine hippurate and ciprofloxacin prophylaxis.

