
#### **Background**

URINARY TRACT INFECTIONS ASSOCIATED WITH SHORT-TERM INDWELLING CATHETERIZATION: Catheter-associated urinary tract infection (UTI) is the most common nosocomial infection in the United States. The risk of UTI in women following pelvic reconstructive surgery is 9-48%. Almost 50% women who undergo pelvic reconstructive surgery develop urinary retention that requires short-term catheterization. (2) In a recent study, over 80% women who required catheterization after pelvic reconstructive surgery used an indwelling catheter for at least 24 hours. (5) The risk of bacteriuria is estimated to be 5-10% for each day of indwelling catheterization. (6,7) UTIs occur frequently after catheter removal, (8,9) likely due to dislodgement of bacterial colonization in biofilms in the catheter. COMPLICATIONS AND COSTS ASSOCIATED WITH UTI: Prevention of post-operative UTI is important for both patient and health care systems. UTIs increase the economic

burden on both patients and physicians, as each episode of UTI costs approximately \$600. (10) Complications from short-term catheterization include pyelonephritis, perinephric abscesses, and bacteremia (UTIs are the cause of 15% of all nosocomial bloodstream infections). (11) Catheter-associated UTI (CAUTI) has become costly for hospitals as well; since October 1, 2008, the Centers for Medicare and Medicaid Services (CMS) have not provided hospitals compensation for CAUTIs. (10) As part of hospital quality measurement, the National Healthcare Safety Network monitors and reports CAUTIs, and prevention of CAUTI is one of the National Patient Safety Goals set by the Joint Commission.

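### The primary comparison is a relative risk with no margin, confidence limit or decision rule, while the sample size works only for a 15-percentage-point risk difference

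*Combined protocol and SAP*

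**What the plan says.** The Overall objectives ask whether two doses of methenamine hippurate "is non-inferior to the efficacy of a 24-hour course of fluoroquinolones". The Accrual section repeats the non-inferiority design and supplies the sizing inputs:

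- Control rate: in the one study it relies on, "the percentage of patients requiring treatment for UTIs after prophylactic antibiotics was 22"%.
- Margin: "If we assume a non-inferiority margin of 15%, a clinically relevant margin and commonly used in non-inferiority/equivalence trials". Whether the 15% is absolute or relative is not stated.
- Error rates and size: "80% power and a one-sided alpha of 0.025, 120 participants in each arm (total of 240 patients) will be required".

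The Analysis Plan is the only place that describes how the primary outcome will be analysed. Straight after naming that outcome it says "Comparison with fluoroquinolones will be performed using relative risk ratio", and then specifies intention to treat. It does not mention non-inferiority, the 15% margin, an alpha level or a confidence interval. The only hypothesis test it offers for a binary outcome is a general statement: "Categorical variables will be analyzed using chi-squared or Fishers exact test". No section gives a margin on the relative-risk scale.

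**The concern.** A non-inferiority conclusion needs three things fixed in advance: an effect measure, a margin on the same scale, and a rule comparing a confidence limit with that margin. Here the margin sits in one section on an unstated scale, the effect measure sits in another on what proves to be a different scale, and there is no rule. A reader could apply the 15% to the difference in rates, but the plan does not say so, and the analysis it names is something else. The choice therefore stays open until the data are seen.

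Two things are at stake. The power claim belongs to an analysis the plan does not name. And the choice of scale can decide the conclusion, because a fixed relative margin and a fixed absolute margin agree at one control rate only.

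**Working it through.** **Inputs from the Accrual section.** Control rate 22%, margin 15%, one-sided alpha 0.025 (z = 1.960), power 80% (z = 0.842), 120 per arm. Equal true rates in the two arms are assumed; the section does not state this.

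**Step 1: reproduce the stated size.** On the risk difference,

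n = (1.960 + 0.842)² × 2 × 0.22 × 0.78 / 0.15² = 7.849 × 0.3432 / 0.0225 = 119.7 per arm.

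This is the plan's 120, so the 15% was used as 15 percentage points.

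**Step 2: size on the relative-risk scale.** With margin m,

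n = (1.960 + 0.842)² × 2 × (0.78/0.22) / (ln m)² = 55.66 / (ln m)².

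- m = 1.15 (the 15% read as relative): 2,849 per arm
- m = 1.50: 339 per arm
- m = 37/22 = 1.68 (15 points converted at 22%): 206 per arm
- m = 2.00: 116 per arm

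The documents give no relative-risk margin. These values are assumptions, shown as a range.

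**Step 3: operating characteristics at 120 per arm.** Each figure is a sum of binomial probabilities over all 121 × 121 possible outcomes. The risk-difference rule is Newcombe 95% upper limit below +15 points; the relative-risk rule is log-method 95% upper limit below m. A false claim means passing when the true rates are 37% versus 22%.

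| Rule | Power, 22% vs 22% | False claim, 37% vs 22% |
|---|---|---|
| Risk difference, +15 points | 80.6% | 2.7% |
| Relative risk, 1.50 | 39% | 0.6% |
| Relative risk, 1.68 | 57% | 2.6% |
| Relative risk, 2.00 | 80% | 14.0% |

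The Wald interval for the risk difference gives 80.3% and 2.5%. No relative-risk margin gives both 80% power and a 2.5% false-claim rate: holding false claims near 2.5% needs a margin near 1.68, and reaching 80% power needs one near 2.

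**Step 4: how often the choice of scale changes the answer.** With 22% in both arms, the risk-difference rule and the relative-risk rule disagree in 23.5% of trials at m = 1.68 and in 6.7% at m = 2.00. At 1.68 nearly all the disagreement runs one way: the risk difference passes and the relative risk does not.

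A worked case, 30/120 on methenamine versus 26/120 on fluoroquinolone:

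- Risk difference: 25.0% − 21.7% = +3.3 points. The Newcombe upper limit is 0.0333 + √[(0.3344 − 0.2500)² + (0.2167 − 0.1524)²] = +13.9 points, below 15, so non-inferior.
- Relative risk: 30/26 = 1.15. The standard error of its log is √(1/30 − 1/120 + 1/26 − 1/120) = 0.235, and the upper limit is exp(0.143 + 1.960 × 0.235) = 1.83, above 1.68, so not shown.

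**Step 5: if the control rate is not 22%.** The Background says "The risk of UTI in women following pelvic reconstructive surgery is 9-48"%. That describes pelvic reconstructive surgery in general, so the rates below are sensitivity assumptions. A margin of 1.68 equals +6.8 points at a 10% control rate and +20.5 points at 30%.

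| Control rate | Power, risk difference | Power, relative risk 1.68 | True +15 points passes, risk difference | True +15 points passes, relative risk 1.68 |
|---|---|---|---|---|
| 10% | 96% | 26% | 2.6% | 0.05% |
| 22% | 80.6% | 57% | 2.7% | 2.6% |
| 30% | 73% | 74% | 2.6% | 10.5% |
| 35% | 69% | 83% | 2.8% | 19.2% |

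The risk-difference rule loses power as rates rise but keeps its protection against a 15-point excess. The relative-risk rule does not.

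**The case against.** The strongest reply is that the plan is recoverable. The Accrual section already gives the margin, the one-sided alpha and the size. Since 120 reproduces only as an absolute margin, its scale is effectively settled. The relative risk may be meant purely as a summary measure, since the same phrase recurs for the culture-positive outcome. On that reading, the Accrual margin applied to the difference in rates gives 80.6% power and nothing is lost.

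The point about scale stands: the intended margin can be inferred. But inferring it by back-calculation is not prespecification, and the Analysis Plan names a different measure for this very comparison. If the relative risk is only descriptive, the plan has no primary non-inferiority analysis at all, which is no better.

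It is also fair that the relative-risk margins are assumed, that the disagreement rate depends on which is chosen, and that at 22% with a margin of 1.68 the relative-risk rule costs power without raising false claims. Inflation needs higher control rates or a looser margin. These points limit the size of the effect. They do not supply the missing rule.

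The chi-squared and Fisher sentence is generic and not tied to the primary outcome, so it is a side note only. If a non-significant chi-squared result were nevertheless read as non-inferiority, a true 37% versus 22% would pass in about 27% of trials.

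**Conclusion.** The concern holds and must be fixed. The trial is sized on a 15-point risk difference, and its only named primary comparison is a relative risk with no margin, confidence limit or decision rule. As written, the Analysis Plan cannot deliver the stated non-inferiority conclusion, and the 80% power does not belong to the analysis it names. That rests on the documents' own figures alone (119.7 against 120 per arm).

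The size of the consequence depends on relative-risk margins the documents do not give. At 120 per arm and 22% in both arms, power runs from 39% to 80% for margins of 1.50 to 2.00, against 80.6% on the risk difference; the top of that range comes with a 14.0% false-claim rate.

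**What to change.** In the Analysis Plan, replace the relative-risk sentence for the primary outcome with wording such as:

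> Primary analysis: risk difference (methenamine minus fluoroquinolone) with a two-sided 95% Newcombe confidence interval. Non-inferiority is concluded only if the upper limit is below +15 percentage points. The relative risk with its 95% confidence interval is supportive. A non-significant chi-squared or Fisher test is not evidence of non-inferiority.

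In the Accrual section, state that the 15% margin is absolute, in percentage points on the risk difference. Another standard interval, such as Wald, would also serve if named in advance. Keeping the relative risk as primary would instead require a justified margin and a new sample size.

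The cost is wording in two places, with the same data and the same 120 per arm. A separate conflict needs reconciling for that number to be secure: the Study duration section still gives 72 per arm, at which power on the risk difference would be 58.4%.

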
medication they are taking. The methenamine, ciprofloxacin, and levofloxacin used in this study are all similar in shape, although not in color. Following catheter removal one to two hours after the first dose of medication, patients will be given a white vial or bag with the second dose of medication (if given methenamine or ciprofloxacin) and will be instructed to take second dose of the study medication at home about 12 hour later. As part of standard of care, nurses perform void trials per practice guidelines by backfilling the bladder with 300 cc normal saline, removing the catheter, and prompting the patient to void immediately. If a patient fails her trial of void, majority of the patients at our site are taught intermittent self-catheterization. If an indwelling catheter is replaced, the allocated treatment (drug or placebo) will be re-administered at repeat trial of void/repeat catheter withdrawal. No further drug will be given if the patient performs intermittent self-catheterization after the failed trial of void. FOLLOW UP VISITS: Three weekly follow-up calls and one postoperative visit are planned. It is standard of care of our clinical practices in the office for a clinical urogynecology nurses to routinely contact patients post-surgery to ask about any symptoms or complications from the procedures they underwent. In this study, per routine office practice, urogynecology nurses will call study participants once a week for the first three weeks following surgery. As per routine, using a structured form, patients will be asked about symptoms of UTI, any treatment for UTI, any urine laboratory testing, visits, and treatment for suspected UTI from other providers other than the urogynecology clinic (e.g. ER, primary care doctor), treatment of complications secondary to UTI (such as pyelonephritis and sepsis), and any additional use of antibiotic for infections other than UTI. Questions related solely to the study medication will include compliance with medications given, and side effects within 24 hours of taking medication. At any time during the study, as per standard of care of all urogynecology patients, patients who feel that they may have UTIs will be encouraged to call the urogynecology clinical nurses or the on-call physician with their symptoms. These encounters, any testing, and any empiric treatment are documented in the electronic medical system. If the diagnosis of UTI is unclear at any time, per standard of care, the patient will be asked to come into the office for physical examination and further diagnostic testing. If patients are suspected of having UTI, treatment for UTI will be initiated. As per routine office care for treatment of UTI, if possible, all patients will be asked to give a specimen for urinalysis and urine culture prior to beginning empiric treatment. Four to eight weeks following surgery, as per standard of care, patients will return to the office for a routine post-operative assessment with the investigating physicians. The patients will undergo routine post-operative physical examination and answer the above questions. Any methenamine or ciprofloxacin that has not been taken as instructed will be returned at this time. At their post-operative visit, the patient will be asked if they were aware of which medication they were taking to assess blinding.

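### Intention to treat is the only analysis set named for the non-inferiority claim; a supporting per-protocol analysis could be pre-specified cheaply from data already collected

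*Combined protocol and SAP*

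**What the plan says.** Accrual sets the hypothesis: "This trial will be an non-inferiority trial", with a 15% margin, one-sided alpha 0.025, 80% power and 120 patients per arm. The Analysis Plan then gives one analysis set, "Analysis will be performed by intention to treat", and repeats it for culture-positive infection. Its comparison is "Comparison with fluoroquinolones will be performed using relative risk ratio", and it does not mention the margin. No section defines a per-protocol or as-treated set, or a sensitivity analysis by adherence.

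Procedures describes exposure as follows.
- Allocation: "At the time of catheter removal, subjects will be randomized to either methenamine hippurate or fluoroquinolones".
- First dose: nurses "distribute the allocated medication to the patient, who will take one dose at the office".
- Second dose: methenamine and ciprofloxacin patients are "instructed to take second dose of the study medication at home about 12 hour later".
- Comparator at some sites: "the 24 hour course of fluoroquinolone used will be one dose of 500 mg of levofloxacin". At the others: "two doses of 500 mg of ciprofloxacin, 12 hours apart".

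Compliance is recorded through returned drug, weekly calls and visits (Secondary outcome variable(s); Procedures). The calls also ask about antibiotics taken for other infections (Procedures). Compliance serves only a descriptive secondary aim (Objectives), and no analysis of the other antibiotic use is described.

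**The concern.** In a superiority trial, influences that make the arms alike usually work against the claim. In a non-inferiority trial they can work for it. Here those influences would be non-study antibiotics in either arm, and second doses missed in both arms at the ciprofloxacin sites.

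The opposite pull also exists. At the levofloxacin sites only methenamine patients have a home dose, so missing it can only hurt methenamine and works against non-inferiority.

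From the intention-to-treat result alone, a reader cannot tell which way this went, or whether the conclusion also holds in patients who took the regimens as assigned. A set of compliant patients defined after the results are known would be open to challenge; one defined now would not be, on that ground.

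**Working it through.** **Inputs from Accrual.** Control rate 22%, margin 15%, one-sided alpha 0.025, power 80%, 120 per arm. (Study duration still gives 144 in total. I use 240, which Accrual derives.)

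**1. The plan's own figure.** n per arm = 2 × 0.22 × 0.78 × (1.960 + 0.842)² / 0.15² = 119.7, rounded up to 120. The stated size is reproduced, so the margin is an absolute difference of 15 percentage points. The rule it implies is non-inferiority if the upper limit of the two-sided 95% CI for the risk difference is below 15 points. The Analysis Plan does not state that rule.

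**2. Nominal false-claim rate.** Summing exact binomial probabilities over all outcomes, with a Wald interval, true rates 37% and 22% and 120 per arm, gives 2.49%. In steps 3 and 4, a false claim means one made when the difference under full adherence is 15 points.

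**3. Missed second doses, by site.** All three inputs are assumptions: f, the share missing the dose (10-20%); c, the share of patients at ciprofloxacin sites (25-75%); and r, the infection rate in methenamine patients who miss it at levofloxacin sites. At ciprofloxacin sites, missing the dose is taken to halve the difference between arms.

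Methenamine rate = c × [0.22 + 0.15 × (1 − f/2)] + (1 − c) × [0.37 × (1 − f) + r × f]

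| Assumed r | False-claim rate over f = 10-20%, c = 25-75% |
|---|---|
| 37% (missed dose has no effect) | 2.7-3.9% |
| 44% | 1.9-3.4% |
| 52% | 1.1-2.9% |

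- Lowest corner (r = 52%, f = 20%, c = 25%): 0.25 × 0.355 + 0.75 × 0.400 = 0.389, giving 1.1%.
- Highest corner (r = 37%, f = 20%, c = 75%): 0.75 × 0.355 + 0.25 × 0.370 = 0.359, giving 3.9%.

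The direction depends on r and c, and the documents give neither.

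**4. Upper case.** Let a share f of patients carry no difference between arms, which would need heavy non-study antibiotic use. The methenamine rate is 0.22 + 0.15 × (1 − f) = 35.5/34.75/34.0% for f = 10/15/20%. The false-claim rate is 4.4/5.8/7.5%.

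**5. Precision of a per-protocol set.** With true rates of 22% in both arms and 10/15/20% excluded, 108/102/96 per arm remain. Power is 76/74/71%, against 80% with 120.

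**6. Bias of a per-protocol set.** Suppose only methenamine patients are excluded, at higher risk, while the overall methenamine rate is 37%. The rate in those kept is (0.37 − r × f)/(1 − f), where r is now the assumed rate in those excluded.
- f = 10%, r = 40%: 0.330/0.90 = 36.7%, 108 against 120 patients, false-claim rate 2.9%.
- f = 15%, r = 48%: 0.298/0.85 = 35.1%, 102 against 120 patients, false-claim rate 5.2%.

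Intention to treat stays at 2.5% in this scenario.

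**The case against.** The strongest reply is that nothing here is an error. Intention to treat keeps the randomised comparison and answers the question of policy. If missed doses shrink the real-world difference below 15 points, a non-inferiority conclusion about that policy is not false. Exposure to non-adherence is also limited: the course lasts 24 hours, the first dose is taken in the office, and the levofloxacin regimen has no second dose. The site scenario straddles the nominal rate, and the per-protocol set can itself lean towards non-inferiority. All of this stands. It is why the point is a supporting analysis and why intention to treat should stay primary.

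A reader might infer two stronger things. One is that intention to treat is the wrong primary analysis for a non-inferiority trial; nothing in the protocol shows that. The other is that non-adherence pushes the result towards non-inferiority here, perhaps to a false-claim rate of 7.5%. The documents do not support that: the direction differs by site comparator, and the larger figures need a share of patients with no difference at all, for which the protocol gives no evidence.

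How unknown three-week outcomes are counted is a separate, minor point. The calls, the post-operative visit and chart review can recover many of them, and it adds no weight here.

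**Conclusion.** The omission is real, and repairing it is a cheap improvement rather than the correction of an error. The plan names one analysis set for its central claim and leaves relevant data unused. Against a nominal 2.5%, the false-claim rate is 1.1-3.9% across the missed-dose scenarios and 4.4-7.5% in the upper case.

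These are scenarios only. They rest on assumed adherence, site mix, infection rates in patients who miss the dose, and a halving of the difference at ciprofloxacin sites. They also rest on a margin rule inferred from Accrual. Neither the direction nor the size can be settled from the documents.

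**What to change.** Change the Analysis Plan in two steps, in this order.

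1. **Primary analysis.** State that the intention-to-treat analysis reports the risk difference with a two-sided 95% CI, that non-inferiority is concluded if the upper limit is below 15 percentage points, and that the relative risk is reported alongside. Without this, the supporting analysis would have a decision rule that the primary lacks.

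2. **Supporting analysis.** Add the same risk difference and CI in a per-protocol set fixed before unblinding: eligible; allocated regimen taken as defined for that site; no non-study antibiotic for another indication before the outcome; three-week status known. Write into the definition now how to classify repeat courses after a catheter is replaced and stopping for side effects, since Procedures and Potential Study Risks provide for both. Report exclusions by arm and by site comparator. State that a per-protocol success does not rescue an intention-to-treat failure, and that a wider interval alone is not a contradiction.

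The cost is one paragraph and a little analysis, with no new data, patients or visits. The plan should state the downsides. Power is lower (step 5). With equal drugs and random exclusion of 10/15/20%, the per-protocol analysis fails in about 8/11/14% of intention-to-treat successes from lost precision alone (simulation). Unequal, outcome-related exclusions can favour non-inferiority (2.9-5.2% in the assumed cases of step 6).
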